6.4.1.1.3 Adverse Events of Special Interest

Participants will be assessed for diagnosis of an AESI at all study visits. AESIs include PIMMCs, AEs specific to COVID-19, or other potential AEs that may be determined at any time by regulatory authorities as additional information concerning COVID-19 is obtained. Given the concern for cytokine storm, an AESI of cytokine release syndrome will be included as an AE specific to COVID-19. Listings of AESI are presented in Section 9.5, Appendix 4.

6.4.1.1.4 Medically Attended Adverse Events

MAAEs are defined as AEs with medically-attended visits including hospital, emergency room, urgent care clinic, or other visits to or from medical personnel for any reason. Routine study visits (including COVID-19 Surveillance Visits) will not be considered medically attended visits. MAAEs are to be reported from the time of first study vaccination until Day 35. MAAEs related to study vaccination are to be reported from the time of first study vaccination until completion of the participant's last study-related procedure, which may include contact for safety follow-up.

6.4.1.1.5 Pregnancy

Pregnancy is not considered an AE unless there is a suspicion that an investigational vaccine may have interfered with the effectiveness of a contraceptive medication. Any pregnancy that occurs during study participation must be reported using a clinical study pregnancy form. To ensure participant safety, each pregnancy must be reported to Novavax, Inc. within 2 weeks

SARS-CoV-2 rS Vaccine Novavax, Inc.

Confidential Version 2.0 – 23 October 2020

of learning of its occurrence. If pregnancy occurs, further study vaccination will be discontinued. The pregnancy must be followed up to determine outcome (including spontaneous miscarriage, elective termination, normal birth, or congenital abnormality) and the status of both mother and child, even if the participant was discontinued from the study. Pregnancy complications and elective terminations for medical reasons must be reported as an AE or SAE. Spontaneous miscarriages must be reported as an SAE.

Any pregnancy brought to the investigator's attention after the participant has completed the study but occurring while the participant was in the study must be promptly reported to:

Sponsor Safety Monitor:

6.4.1.2 Eliciting and Documenting Adverse Events

At every study visit, participants will be asked a standard question to elicit any medicallyrelated changes in their well-being. They will also be asked if they have been hospitalised, had any accidents, used any new medications, or changed concomitant medication regimens (both prescription and OTC medications).

In addition to participant observations, AEs will be documented from any data collected on the AE page of the eCRF or other documents that are relevant to participant safety.

6.4.1.3 Reporting Adverse Events

All AEs reported or observed during the study will be recorded on the AE page of the eCRF. Information to be collected includes study vaccine, type of event, time of onset, dosage, investigator-specified assessment of severity and relationship to study vaccine and/or study procedure, time of resolution of the event, seriousness, any required treatment or evaluations, and outcome. Any AEs resulting from concurrent illnesses, reactions to concurrent illnesses, reactions to concurrent medications, or progression of disease must also be reported. All AEs will be followed until they are resolved, stable, or judged by the investigator to be not clinically significant. The Medical Dictionary for Regulatory Activities (MedDRA) will be used to code all AEs.

Any medical condition that is present at the time that the participant is screened but does not deteriorate should not be reported as an AE. However, if it deteriorates at any time during the study, it should be recorded as an AE.

Any AE that is considered serious by the investigator or that meets SAE criteria (Section 6.4.1.1.1) must be reported to the sponsor within 24 hours after the investigator has confirmed the occurrence of the SAE. The investigator will provide a causality assessment (whether there is a reasonable possibility that the study vaccine caused the event) to the study vaccine. The sponsor will be responsible for notifying the relevant regulatory authorities of any SAE, in compliance with health authority requirements, as outlined in the relevant clinical study guidelines.

For this study, the following contact information will be used for SAE reporting:

Phone:	
Fax:	
Email:	

6.4.1.4 Assessment of Severity

The severity (or intensity) of an AE refers to the extent to which it affects the participant's daily activities and will be classified as mild, moderate, or severe using the following criteria:

- Mild (grade 1): These events require minimal or no treatment and do not interfere with the participant's daily activities.
- Moderate (grade 2): These events result in a low level of inconvenience or require minor therapeutic measures. Moderate events may cause some interference with normal functioning.
- Severe (grade 3): These events interrupt a participant's usual daily activity and may require systemic drug therapy or other treatment. Severe events are usually incapacitating.

If the severity of an AE changes, the most intense severity should be reported. An AE characterised as intermittent does not require documentation of the onset and duration of each episode.

6.4.1.5 Assessment of Causality

The investigator's assessment of an AE's relationship to study vaccine is part of the documentation process, but it is not a factor in determining what is or is not reported in the study. If there is any doubt as to whether a clinical observation is an AE, the event should be reported.

The investigator will assess causality (i.e., whether there is a reasonable possibility that the study vaccine caused the event) for all AEs and SAEs (solicited reactions are to be considered as being related to study vaccination). The relationship will be classified as follows:

- Not related: There is not a reasonable possibility of relationship to study vaccine. The AE does not follow a reasonable temporal sequence from administration of study vaccine or can be reasonably explained by the participant's clinical state or other factors (e.g., disease under study, concurrent diseases, and concomitant medications).
- Related: There is a reasonable possibility of relationship to study vaccine. The AE follows a reasonable temporal sequence from administration of study vaccine and

cannot be reasonably explained by the participant's clinical state or other factors (e.g., disease under study, concurrent diseases, or concomitant medications), represents a known reaction to study vaccine or other vaccines in its class, is consistent with the known pharmacological properties of the study vaccine, and/or resolves with discontinuation of the study vaccine (and/or recurs with re-challenge, if applicable).

6.4.1.6 Follow-up of Adverse Events

All AEs must be reported in detail on the appropriate page of the eCRF and followed until they are resolved, stable, or judged by the investigator to be not clinically significant.

6.4.2 Vital Sign Measurements

Vital sign measurements will include oral temperature (or via forehead/ear reader), pulse rate and diastolic and systolic blood pressure (after participant is seated for at least 5 minutes), and pulse oximetry. Temperature will be recorded and graded during general systemic reactogenicity evaluation (Section 6.4.1.1.2). The other vital sign measurements will be recorded as continuous variables prior to each study vaccination. Pulse oximetry and other vital signs will be taken on room air.

On study vaccination days, vital sign measurements will be collected once before study vaccination to ensure participant has controlled blood pressure and heart rate and no evidence of fever prior to study vaccination and once more, at approximately 15 to 30 minutes after study vaccination, to check for any reactions to the study vaccine. The investigator will only apply standard toxicology grading on the day of study vaccination, both before and after study vaccination (Section 9.4, Appendix 3). If individual vital sign measurements are considered clinically significant by the investigator, study vaccination may be withheld that day, and participants may return on a subsequent day for re-evaluation and study vaccination, ideally, within the time window specified in the SOE (Table 3-1).

6.4.3 Physical Examinations

A physical examination will be performed at screening/Day 0 (at minimum, assessment of skin, head, ears, eyes, nose, throat, neck, thyroid, lungs, heart, cardiovascular, abdomen, lymph nodes of the upper extremities and neck, and musculoskeletal system/extremities). Height and weight will be measured at screening only.

A targeted or symptom-directed physical examination will be performed at the time points specified in the SOE (Table 3-1). Special attention should be made to examine the lymph nodes of the upper extremities on vaccination days and the respiratory system at all COVID-19 Surveillance Visits.

6.4.4 Safety Monitoring

Safety oversight will be conducted by an SMC during the course of the study. The SMC is an independent group of experts that monitors participant safety and advises the sponsor. The SMC members will be separate and independent of site personnel participating in this study and should not have a scientific, financial, or other conflict of interest related to this study or the sponsor. The SMC will consist of members with appropriate expertise to contribute to the interpretation of the data from this study.

A global SMC was convened to oversee the safety of the ongoing Phase 1/2 study (Protocol 2019nCoV-101) and will oversee 1 or more additional studies across the SARS-CoV-2 rS vaccine program. A separate SMC will be convened for this study. The designated SMC will monitor the safety of participants in the study and will follow an SMC charter. The SMC will review blinded and unblinded safety and reactogenicity data. The SMC will also review sufficient clinical event data to ensure detection of evidence of enhanced disease. The SMC will convene to perform safety reviews on a scheduled basis as per the SMC charter; for immediate concerns regarding safety observations during this study; and as needed.

The SMC will operate under the rules of a sponsor-approved charter that will be approved at the organisational meeting of the SMC. At this time, each data element that the SMC needs to assess will be clearly defined. Procedures for SMC reviews/meetings will be defined in the charter. The SMC will review applicable data for safety assessments (AEs by classifications) and any clinical data that may be of significance to this review (e.g., demographics, study vaccination timing, and medications). Additional data may be requested by the SMC, and interim statistical reports may be generated as deemed necessary and appropriate for this review. The SMC may receive data in aggregate and presented by study vaccine group. The SMC may also be provided with expected and observed rates of the expected AEs in an unblinded fashion and may request the study vaccine assignment be unblinded for an individual participant if required for safety assessment.

7. STATISTICAL ANALYSIS PLANS

7.1 Sample Size Calculations

This study is designed to enrol approximately 15,000 participants, randomised 1:1 into the 2 study vaccine groups. The sample size is driven by the total number of events expected to achieve statistical significance for the primary efficacy endpoint; a target of 152 primary endpoints, the mild, moderate, or severe COVID-19 cases. The target number of events of 152 was chosen to provide 90% overall power for a 60% vaccine efficacy (VE) (Table 7-1). Two formal interim analyses of efficacy and futility will be conducted based on the accumulation of approximately 43% (66 events) and 72% (110 events) of the total anticipated primary endpoints using O'Brien-Fleming boundary conditions. Power calculations were performed by 10,000 simulated trials that were created under various assumptions of VEs and analyzed using methods described in the "efficacy analysis" section without covariates. A 90% evaluability rate for the per-protocol (PP) efficacy (PP-EFF) population (assuming 10% unevaluable due to attrition and/or baseline-seropositive participants) was used for the power calculations. All simulations were performed in SAS V9.4.

Assumed Vaccine Efficacy		Estin	nated Power	
Symptomatic COVID-19 Illness	Planned Interim Analyses			Overall (At Either
PCR-Confirmed SARS-CoV-2 Infection	First (43%)	Second (72%)	At Final Analysis	Interim Analysis or Final Analysis)
50%	1%	19%	29%	49%
55%	2%	34%	36%	72%
60%	7%	53%	31%	90%
65%	16%	65%	17%	98%
70%	31%	64%	5%	>99%
75%	55%	45%	1%	>99%
80%	80%	20%	0%	>99%

 Table 7-1
 Power Under Various Vaccine Efficacy Assumptions

Abbreviations: COVID-19 = coronavirus disease 2019; PCR = polymerase chain reaction; SARS-CoV-2 = severe acute respiratory syndrome coronavirus 2

7.2 Analysis Sets

The all-randomised set will include all participants who were randomised regardless of the receipt of any study vaccine (SARS-CoV-2 rS with Matrix-M1 adjuvant or placebo). The all randomised set will be used for the subject disposition summaries.

SARS-CoV-2 rS Vaccine Novavax, Inc. Confidential Version 2.0 – 23 October 2020

The intent-to-treat (ITT) analysis set will include all participants who are randomised and receive at least 1 dose study vaccine (SARS-CoV-2 rS with Matrix-M1 adjuvant or placebo), regardless of protocol violations or missing data. The ITT analysis set will be used as a supportive analysis population for the immunogenicity and efficacy analyses and will be analysed according to the study vaccine group as randomised.

The safety analysis set will include all participants who receive at least 1 dose of study vaccine (SARS-CoV-2 rS with Matrix-M1 adjuvant or placebo). Participants in the safety analysis set will be analysed according to the study vaccine actually received.

The PP-EFF will include baseline seronegative participants who receive both doses of study vaccine (SARS-CoV-2 rS with Matrix-M1 adjuvant or placebo) and have no major protocol deviations that occur before the first COVID-19 episode affecting the primary efficacy outcome as assessed by the sponsor prior to unblinding. All analyses of the PP-EFF population will also exclude any illness episodes with positive SARS-CoV-2 by any validated PCR or antibody test occurring before 7 days after second study vaccination (e.g., Day 28).

The per-protocol immunogenicity (PP-IMM) analysis set for each post-randomisation visit will include participants who receive scheduled dose(s) of study vaccine (SARS-CoV-2 rS with Matrix-M1 adjuvant or placebo), have at least a baseline and the serum sample result for the visit available after study vaccination, and have no major protocol violations that are considered clinically likely to impact the immunogenicity response at the corresponding study visit as assessed by the sponsor prior to unblinding. For each visit, the SARS-CoV-2 unexposed population will also exclude any illness episodes with positive SARS-CoV-2 by any validated PCR or antibody test prior to each visit. Prior exposed participants will be determined using baseline SARS-CoV-2 immunity defined as positive SARS-CoV-2 by PCR or serum IgG antibody at baseline, or positive SARS-CoV-2 by qualitative PCR through Day 35, according to the specified analysis. Analysis will be performed to assess if immune responses differ between exposed and unexposed individuals (i.e., whether prior exposure alters dosing regimen considerations in a pandemic response).

The review and determination for exclusion from the PP populations will be carried out in a blinded fashion by a study clinician prior to unblinding for each interim analysis based on all available information from the locked database. Both PP populations will be analysed according to the study vaccine group as randomised.

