5.3.2 Breaking the Blind

A participant's study vaccine assignment will not be broken until the end of the study for the clinical site study team unless medical treatment of the participant depends on knowing the study vaccine the participant received. In the event that the blind needs to be broken because of a medical emergency, the investigator may unblind an individual participant's study vaccine allocation.

Whenever possible, the investigator should contact the medical monitor to discuss the medical emergency and the reason for revealing the actual study vaccine received by that participant. In the event that the investigator cannot contact the medical monitor in a timely manner the blind may be broken by the investigator. The medical monitor should be contacted as soon as feasible after the unblinding. The study vaccine assignment will be unblinded through IRT. Reasons for study vaccine unblinding must be clearly explained and justified in the eCRF. The date on which the code was broken together with the identity of the person responsible must also be documented.

In the event that a safe and effective vaccine against SARS-CoV-2 is licensed and made widely available during the course of the study, a discussion with appropriate regulatory agencies will take place to discuss if the blind should be broken to offer vaccine to placebo participants.

The blind may also be broken in the event of a Suspected Unexpected Serious Adverse Reaction (SUSAR) to determine regulatory reporting.

In addition to the aforementioned situations where the blind may be broken, the data will also be unblinded to a statistical team at specified time points for planned analyses prior to study completion, as outlined in Section 7.6.

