5.5 Concomitant Medications and Prohibitive Therapy

5.5.1 Concomitant Medications

Administration of medications, therapies, or vaccines will be recorded in the eCRF. Concomitant medications will include all medications (including vaccines) taken by the participant from the time of signing the ICF through EOS (or through the early termination visit if prior to that time). Prescription and over-the-counter (OTC) drugs, as well as herbals, vitamins, and supplements, will be included.

5.5.2 **Prohibitive Therapy**

- No live vaccine will be allowed within 4 weeks of first study vaccination until 28 days after second study vaccination (Day 49).
- No vaccine (except for a licensed seasonal influenza vaccine and participants in the seasonal influenza co-administration sub-study) will be allowed within 2 weeks of first study vaccination until 28 days after second study vaccination (Day 49).

No influenza vaccine (except participants in the seasonal influenza co-administration sub-study) will be allowed 7 days before each vaccination.

NOTE: Participants in the seasonal influenza co-administration sub-study will be allowed to have the co-administration of a licensed seasonal influenza vaccine at the same time as first study vaccination.

- No unlicensed vaccine should be given within 45 days prior to first study vaccination until after the last study visit.
- No investigational product (drug/biologic/device) within 45 days prior to first study vaccination until after the last study visit.
- No chronic administration (defined as more than 14 continuous days) of any immunosuppressant medication within 3 months of first study vaccination until the last study visit (except topical steroids or short-term oral steroids with course lasting ≤ 14 days). The use of topical, inhaled, and nasal glucocorticoids will be permitted if other chronic disease conditions are not exclusionary.
- No continuous use of anticoagulants, such as coumarins and related anticoagulants (i.e., warfarin) or novel oral anticoagulants/anti-platelet agents. Use of ≤ 325 mg of aspirin per day as prophylaxis is permitted.

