7.3 Statistical Analysis

Details of all statistical analyses will be described in the SAP.

All data collected will be presented in data listings. Data from participants excluded from an analysis set will be presented in the data listings but not included in the calculation of summary statistics for that analysis set.

For categorical variables, frequencies and percentages will be presented. Continuous variables will be summarised using descriptive statistics (number of participants, mean, median, minimum, and maximum).

Baseline demographic and background variables will be summarised by study vaccine group. The number of participants who enrol in the study and the number and percentage of participants who complete the study will be presented. Frequency and percentage of participants who withdraw or discontinue from the study, and the reason for withdrawal or discontinuation, will also be summarised.

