7.3.1 Efficacy Analyses

The primary endpoint will be analysed on the PP-EFF Analysis Set and supported by analysis of the ITT Analysis Set. Conclusions concerning declaration of attainment of the primary endpoint at the completion of the study will only be based on the PP-EFF population.

VE is defined as VE $(\%) = (1 - RR) \times 100$, where RR = relative risk of incidence rates between the 2 study vaccine groups (SARS-CoV-2 rS with Matrix-M1 adjuvant or placebo). The final analysis for the primary objective in the PP-EFF population will be carried out at the overall one-sided Type I error rate of 0.025 for the 3 planned analyses. The nominal alpha to be spent for the final analysis will be recalculated using the Lan-DeMets alpha spending function based on the actual numbers of events used for the interim analyses and the numbers of endpoints to be used for the final analysis. The estimated RR and its CI will be derived using Poisson regression with robust error variance [Zou 2004]. The explanatory variables in the model will include study vaccine group. The dependent variable will be the incidence rate of the endpoint of interest. The robust error variances will be estimated using the repeated statement and the participant identifier. The Poisson distribution will be used with a logarithm link function. The site (depending on the distribution of endpoints) and the age strata will be included in the model as covariates. To assess incidence rates rather than absolute counts of cases, accounting for differences in follow-up times starting with 7 days after the second vaccination among participants, an offset will be utilized in the Poisson regression. In case the total number of events to be analysed may be too low for an asymptotic method proposed (i.e., ≤ 5 events in either treatment group), an alternative method based on the single sample exact binomial distribution may be used for the analysis. This method is based on the proportion of the events in the SARS-CoV-2 rS with Matrix-M1 adjuvant group among the total number of events observed in both treatment groups after

SARS-CoV-2 rS Vaccine Novavax, Inc.

adjusting for the differential number of subjects (or inclusive of differential lengths of follow-up) between the 2 treatment groups.

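### Section 7.2 makes PP-EFF membership depend on whether a major deviation preceded the participant's own COVID-19 episode, and states no censoring for deviators who never have one

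*Protocol*

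**What the plan says.** Section 7.2 requires that PP-EFF participants "have no major protocol deviations that occur before the first COVID-19 episode affecting the primary efficacy outcome". The cut-off is thus each participant's own first episode, not a fixed study day. The section does not say what happens to a participant who deviates and has no episode.

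Section 7.3 describes what exclusion from a set means for that set's summary statistics: "Data from participants excluded from an analysis set will be presented in the data listings but not included in the calculation". Section 7.3.1 has follow-up enter the Poisson model through an offset that starts 7 days after the second vaccination. It names no deviation as an end to that follow-up.

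The weight on this set is explicit in Section 7.3.1: "Conclusions concerning declaration of attainment of the primary endpoint at the completion of the study will only be based on the PP-EFF population". Section 7.5 ties early stopping for efficacy to the same set.

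Two safeguards are stated. The exclusion review is "carried out in a blinded fashion by a study clinician prior to unblinding for each interim analysis based on all available information" (Section 7.2). There is also a second analysis: "The primary endpoint will be analysed on the PP-EFF Analysis Set and supported by analysis of the ITT Analysis Set" (Section 7.3.1).

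**The concern.** Take a participant with a major deviation at month 4. If COVID-19 occurred at month 2, the deviation came after the episode, so the participant stays in and counts as a case. If no COVID-19 occurred, the rule does not settle what happens, and two literal readings are open:

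- **Reading A.** Any deviation in a non-case disqualifies, and the participant's whole follow-up goes. Cases before a deviation are kept while disease-free time from deviators is discarded, so the rate in that arm is overstated.
- **Reading B.** Without an episode there is nothing for the deviation to precede, so non-cases are never excluded. Only cases with an earlier deviation are lost, so the rate is understated.

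Either way, two participants with the same deviation history are treated differently because of the outcome. If late deviations are not equally common in the two arms, the distortion does not cancel in the relative risk that is tested against the 30% null.

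Late deviations are possible by design. Some Section 5.5.2 restrictions run to the end of follow-up, for example "No investigational product (drug/biologic/device) within 45 days prior to first study vaccination until after the last study visit".

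**Working it through.** **Inputs from the protocol.** 1:1 allocation; 152 events with looks at 66 and 110; one-sided alpha 0.025; null VE of 30% or less; nominal alphas 0.00063, 0.00804 and 0.02246 (Sections 7.1, 7.3.1 and 7.5).

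**Step 1: reproduce the stated design.** Given the total number of events, vaccine-arm events are binomial with p = RR/(1 + RR). Success requires the upper Wald limit for log RR, at the nominal alpha, to fall below log 0.70. The largest vaccine-arm counts that succeed are 13 of 66, 32 of 110 and 50 of 152. These are VE boundaries of 75.5%, 59.0% and 51.0%, against about 75%, 59% and 51% in Table 7-2. At a true VE of 60%, the exact three-look power is 6.9% + 52.7% + 30.3% = 89.9%, against 7%, 53%, 31% and 90% overall in Table 7-1. At a true VE of 30%, one-sided type I error is 0.0237. The design reproduces.

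**Step 2: effect of the rule on one arm's rate.** Assume rare events, constant hazards, and deviations that are independent of infection and reach a proportion q by the end of follow-up. Let d = −ln(1 − q).

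- Under A and B alike, the cases kept are those before any deviation, a fraction (1 − e^−d)/d of all cases.
- Reading A keeps only non-deviators' person-time, a fraction e^−d. Rate multiplier: (e^d − 1)/d.
- Reading B keeps all person-time. Rate multiplier: (1 − e^−d)/d.
- Censoring at the deviation keeps a fraction (1 − e^−d)/d of both cases and person-time. Rate multiplier: 1.

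| q | Reading A | Reading B | Censoring |
|---|---|---|---|
| 2% | 1.010 | 0.990 | 1 |
| 5% | 1.026 | 0.975 | 1 |
| 10% | 1.055 | 0.949 | 1 |

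**Step 3: effect on RR.** Apparent RR = true RR × (vaccine multiplier / placebo multiplier). For 10% placebo and 5% vaccine under A, the factor is 1.0261/1.0546 = 0.973. A true VE of 30% then reads 1 − 0.70 × 0.973 = 31.9%. Under B the factor is 0.9748/0.9491 = 1.027, and it reads 1 − 0.70 × 1.027 = 28.1%.

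**Step 4: operating characteristics with the shifted RR.** All deviation rates are assumptions; the protocol gives none.

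| Placebo / vaccine | Reading | VE 30% reads | VE 60% reads | Type I error | Power at VE 60% |
|---|---|---|---|---|---|
| equal, e.g. 5/5 or 10/10% | A or B | 30.0% | 60.0% | 0.024 | 90% |
| 5/2% | A | 31.1% | 60.6% | 0.029 | 91% |
| 5/2% | B | 28.9% | 59.4% | 0.019 | 88% |
| 10/5% | A | 31.9% | 61.1% | 0.034 | 92% |
| 10/5% | B | 28.1% | 58.9% | 0.016 | 87% |
| 5/10% | A | 28.1% | 58.9% | 0.016 | 87% |
| 5/10% | B | 31.8% | 61.1% | 0.034 | 92% |
| any of these | censoring | 30.0% | 60.0% | 0.024 | 90% |

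**The case against.** **Direction.** A reader might infer that the rule inflates VE. The text does not support this: the same imbalance raises VE under A, lowers it under B, and has no effect with censoring. Equal rates cancel. In an observer-blind trial whose restrictions apply to both arms alike, nothing in the protocol says that late deviations are commoner on placebo. All of this stands.

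**A placebo-only mechanism.** A reader might point to Section 5.3.2, which foresees a discussion with regulators "to discuss if the blind should be broken to offer vaccine to placebo participants". That commits only to a discussion, and only if a safe and effective vaccine is licensed and widely available. Section 5.5.2 bars licensed vaccines only to Day 49, so a licensed COVID-19 vaccine taken later is not clearly a deviation and may never engage the quoted rule. The section therefore cannot carry a claim of one-sided bias. It does show that the handling of such follow-up needs to be stated.

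**Large error rates.** Assuming 20% vs 10% late deviators under A gives a type I error of 0.052, and 25% vs 10% gives 0.077. No document supports rates of that order. Only major deviations affecting the primary outcome count. Follow-up may also be short: at 5% annual incidence, 13,500 evaluable participants and VE 60%, expected events are 13,500 × 0.05 × (1 + 0.4)/2 = 472.5 per year. The 152 events then need 152/472.5 = 0.32 years, about 3.9 months. Lower incidence lengthens this.

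**Safeguards.** Blinded review stops a reviewer favouring an arm, but not selection by a rule that itself refers to the outcome. The supportive ITT analysis ignores deviations, so comparing it with PP-EFF could reveal a distortion. It cannot correct the decision.

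**The SAP.** Person-time rules often sit there, and the exclusion sentence in Section 7.3 speaks of summary statistics, not of the offset. This is fair as regards detail. But the protocol does not leave membership open: it fixes a criterion tied to the episode.

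**Conclusion.** The point holds as an outcome-dependent and incomplete definition of the only decisive analysis set. It is not a demonstrated inflation of VE. Bias in RR requires late deviations to be unequally common in the two arms, and its sign depends on the reading and on which arm deviates more. For assumed splits of 5/2% and 10/5% (placebo/vaccine), a true VE of 30% shifts by about 1 to 2 points. One-sided type I error is about 0.029 to 0.034 under whole removal of non-case deviators. It is about 0.019 to 0.016, with power of about 88% to 87%, if only cases can be excluded. These figures rest on rare events, constant hazards and deviations unrelated to infection risk. They are a sensitivity range, not a forecast. One sentence that permits opposite biases in the primary set is worth correcting before the first interim analysis.

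**What to change.** In Section 7.2, define PP-EFF membership using only major deviations up to 7 days after the second vaccination. Treat any later major deviation affecting the primary outcome as a censoring date that ends the follow-up time in the Poisson offset, for cases and non-cases alike. State the same censoring for individual unblinding and for receipt of a non-study COVID-19 vaccine, whether or not either is classed as a deviation, since Section 5.5.2 does not clearly settle this after Day 49.

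Under the assumptions above, this returns the rate multiplier to 1 in both arms and type I error to about 0.024 for every split tried. The cost is a sentence or two; vaccinations and unblinding dates are already recorded (Sections 5.5.1 and 5.3.2), and deviations are documented (Section 9.3.3.2.2). A case occurring after a late deviation is not counted, but that is already so under the current rule. Compared with whole-participant removal, the change recovers person-time. The 152-event target and the stated 90% power do not change.
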